- Information on risk factors of TE events (e.g., medical comorbidities, treatments and demographic characteristics) approximately 12 months prior to the index date. If the patient is below 1 year of age, the lookback period will be shortened to birth until index date. Anamnestic information capturing historic events but entered in the registry database less than 12 months before the index date will be considered as long as they were recorded prior to the index date;
- Signed the informed consent form where required by local regulations.

Exclusion criteria:

- Development of FVIII inhibitors any time before the index date;
- Treatment with emicizumab at any time before the index date.

Variables

Primary Safety Variables

The primary variables for this study are as follows:

TE events

Secondary Variables

The secondary variables for this study are as follows:

- SAEs
- TMA events
- Serious systemic hypersensitivity reactions, including anaphylaxis
- Demographic characteristics
- Time since diagnosis of congenital HA
- Prior treatments for haemophilia
- HA medical history
- Concomitant medications
- Other medical history and concurrent conditions
- Risk factors for TE events.

Study Size

Projected real-world study size based on feasibility study and existing literature on prevalence of inhibitors and moderate HA population, indicates ~202 patients newly

exposed to emicizumab can be captured with a total study population of 3000 moderate HA patients, within the cohort entry period.

Study size estimations were done via simulations to assess whether the real-world estimate is adequate for the primary objective of estimating the crude incidence rate (IR) of 1st TE events by varying sample size targets, expected event rates and threshold value for 95% Clopper-Pearson confidence interval (CI). Simulations were run to calculate expected accuracy defined as the probability that the CI of the crude IR does not exceed an upper threshold.

Approximately 200 emicizumab exposed patients across all study countries will be necessary with an average follow-up of 4 years for each patient, to achieve 88% probability that the 95% Clopper-Pearson CI of the crude IR does not exceed a threshold value of one event per 100 person-years (PY). This assumes an expected crude IR of TE events of 0.15 events per 100 PY.

Data Analysis

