8.3.2.4. Risk Factor Variables for TE Events

The following candidate variables will be used to characterise the patients TE risk profile and are assessed within one year prior to the index date. The candidate risk factors were chosen based reference literature regarding their relationship with TE events (den Heijer et al., 1996; Goldhaber, 2010; Heit, 2015; Keramidas et al., 2021; Lowe, 2008; Pastori et al., 2023; Raj et al., 2022). As the feasibility assessment did not provide detailed information on the availability of all TE risk factors, a full evaluation of the availability of the risk factors in each data source will be provided in the SAP. Risk factors considered to be included:

Patient characteristics:

- Advanced age (age > 50 years)
- Smoking
- Body Mass Index (BMI) (BMI ≥ 30 kg/m² i.e., obesity)
- Sex

Patient medical history:

- Previous TE event
- Venous insufficiency
- Myocardial infarction
- Ischaemic heart disease
- Coronary artery disease
- Cerebrovascular disease
- Peripheral vascular disease
- Heart failure
- Hypertension
- Atherosclerosis
- Diabetes
- Medical device use
- Moderate or severe liver disease
- Recent hospitalisation/surgery
- Previous or ongoing cancer
- Chronic Inflammatory Lung Diseases (including Chronic obstructive pulmonary disease [COPD], asthma, tuberculosis)
- Obstructive sleep apnea

Hemlibra—F. Hoffmann-La Roche Ltd Protocol BO44691, Version 2.0

- Lower limb paralysis
- Hyperhomocysteinemia
- Chronic kidney disease Stage 3 and above
- Recent trauma/ fractures
- Hormone replacement therapy including oral contraceptives
- Pregnancy/puerperium
- Infectious diseases (including sepsis, pneumonia, Covid-19 infection and Human Immunodeficiency Virus infection)
- Inflammatory disorders (including systemic lupus erythematosus [SLE], inflammatory bowel disease and rheumatoid arthritis)

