8.7.2. Planned Analyses

For the analysis of the primary objective and secondary objectives 1, 2, and 3 the overall crude and crude stratified IRs will be calculated. The person-time of each patient will be based on the follow-up and censoring criteria presented in section 8.2.4. and 8.2.5.

For the calculation of crude IRs, the denominator will be the pooled person-time of all the patients within the cohort. The patient time-at-risk will be calculated from index date until the date of an incident event or censoring, whichever occurs first. All first events occurring during follow-up period will be counted in the total number of events. Crude IRs will be presented per 100 PY with 95% CI.

For the primary objective, the numerator will be the number of first TE events of all patients within the cohort. For secondary objectives 1, 2, 3 the numerator will be the number of first occurrences of any SAE; TMA events or serious systemic hypersensitivity reactions, including anaphylaxis; respectively.

For the analysis of secondary objective 4, calculation of crude stratified IRs of 1st TE events will be done. The events will be counted for each category/stratum of relevant pre-defined risk factors (see section 8.3.2.4. for a listing of considered risk factors). More details on the risk factor based tabulations will be presented in SAP.

For analysis of secondary objective 5, characteristics of TE events, SAEs, TMA, and serious systemic hypersensitivity reactions, including anaphylaxis (e.g., diagnosis and symptoms), will be tabulated. In addition, time to 1st TE event; time to 1st TMA event; time to 1st serious systemic hypersensitivity reactions, including anaphylaxis; and time to any 1st SAE event will be described by Kaplan-Meier curves.

For analysis of secondary objective 6, calculation of crude IR and crude incidence proportion of TE, TMA events, SAEs and serious systemic hypersensitivity reactions, **Hemlibra—F. Hoffmann-La Roche Ltd** Protocol BO44691, Version 2.0

including anaphylaxis, will be calculated and tabulated for FVIII prophylaxis use (yes/no) prior to emicizumab treatment.

Patient demographic and clinical characteristics will also be tabulated in relation to the AEs (TE events, SAEs, TMA events and serious systemic hypersensitivity reactions, including anaphylaxis) and in total.

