8.7.3. Subgroup Analyses

Subgroup analyses will be carried out for all study objectives (section 7). Analyses specific to each group will be prioritised/de-prioritised following review of patient's numbers for each group. Subgroups of interest include, but are not limited to:

- FVIII prophylaxis use prior to emicizumab treatment initiation (yes/no) in line with secondary objective 6.
- Analysis by geographical regions (Europe; US and Canada; Other).
- Cardiovascular disease including treatment for cardiovascular disease, if feasible (yes/no) prior to emicizumab treatment initiation.
- Age at emicizumab treatment initiation (<50, ≥50 years-old).

All variables that are used to define subgroups will be assessed at the index date which is emicizumab treatment initiation. Further details on subgroups, their categories, and criteria for regrouping of any categories will be described in the SAP.

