8.9.2. Information Bias

Information bias is the bias arising from the systematic measurement error or misclassification of patients. As this is a registry-based study the validity of the findings of the study will solely rely on the validity, quality and completeness of the information recorded in the registries. There is potential for heterogeneity in the type of data collected from the registries regarding emicizumab treatment exposure, e.g., the exact dates of dispenses and SC injections, that could potentially result in exposure misclassification that are registry specific. Depending on the registry, specific limitations for exposure classification could be developed to avoid misclassification. There is also potential for heterogeneity in the study population because of different lookback periods when patients enrol in different registries. In certain cases, the lookback period might not be fully 12 months and the inclusion criteria regarding previous HA outcomes and HA treatments approximately 12 months prior to the index date (see section 8.2.6.1.) may not be fully confirmed if emicizumab treatment initiation (index date) coincides with patient enrolment into the registry.

In the primary incidence analysis, we do not exclude patients with a history of TE events before the index date. Thus, there exists a possibility that individuals with prior TE **Hemlibra—F. Hoffmann-La Roche Ltd**

Protocol BO44691, Version 2.0 events are included in the crude IR of TE. In the planned analysis of secondary objective 4 the IR would be tabulated based on the history of TE events during the lookback period. This would ensure that the incidence would be calculated for patients treated with emicizumab without any prior TE events during the lookback period and in addition contribute valuable evidence on the event rate among patients treated with emicizumab who have a history of TE events.

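### The one-year window for every candidate TE risk factor puts older recorded TE, MI or cancer history in the 'absent' stratum of secondary objective 4, and other sections do not match it

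*Protocol*

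**What the plan says.** Section 8.3.2.4 lists the candidate TE risk factors and states once, for the whole list, that they "will be used to characterise the patients TE risk profile and are assessed within one year prior to the index date". The list holds two kinds of item. Some are history of any age by their label: previous TE event, myocardial infarction, and "Previous or ongoing cancer". Others are recent by their label, such as "Recent hospitalisation/surgery". No item has a window of its own.

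Section 8.7.2 says how the list is used for secondary objective 4: "The events will be counted for each category/stratum of relevant pre-defined risk factors", giving a crude rate of first TE per stratum.

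Section 8.9.2 notes that the primary analysis does not exclude patients with a previous TE. It says that under secondary objective 4 "the IR would be tabulated based on the history of TE events during the lookback period", so that a rate is available for patients "without any prior TE events during the lookback period".

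Two other places treat history differently. The inclusion criterion on risk-factor information (Synopsis and section 8.2.6.1) says: "Anamnestic information capturing historic events but entered in the registry database less than 12 months before the index date will be considered", provided the entry precedes the index date. Section 8.7.3 defines a subgroup as "Cardiovascular disease including treatment for cardiovascular disease, if feasible (yes/no) prior to emicizumab treatment initiation", with no one-year limit.

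**The concern.** A one-year window suits transient factors such as surgery, trauma or pregnancy. It does not suit a factor whose meaning is that the event ever happened. A patient whose TE, infarction or cancer occurred and was recorded more than a year before index is placed in the 'absent' stratum for that factor. The 'absent' rate is then pulled up, the contrast between strata shrinks, and the small 'present' stratum becomes smaller.

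This matters most for prior TE, because 8.9.2 offers that stratification as its answer to including such patients in the primary analysis.

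The sections also disagree. Under the anamnestic clause an old event may count if it was entered as history in the year before index. Under 8.3.2.4 the same event, recorded when it happened, apparently does not. Classification could then depend on when a patient enrolled and in which registry. Table 7 shows collection starting between 1968 and 2020, so in a pooled analysis the misclassification need not be the same across registries.

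**Working it through.** The protocol gives no figure for this point, so the check has two parts.

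**1. The sections side by side**

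| Place | Window for history |
|---|---|
| 8.3.2.4, all candidate TE risk factors | one year before index |
| 8.9.2, prior-TE stratum | the lookback period |
| Synopsis and 8.2.6.1, anamnestic clause | historic events, if entered in the 12 months before index |
| 8.7.3, cardiovascular subgroup | before initiation, no limit stated |
| 8.2.6.1, spontaneous bleeding | any time before index |
| 8.2.6.2, bypassing agents and rituximab | any time before index |

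The last two rows show that one year is not a limit of the design as a whole. Section 8.3.2.4 leaves the availability of the factors to the SAP, and 8.7.2 leaves tabulation detail to it. Neither leaves the window open.

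**2. Size**

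From section 8.5.2: 200 patients × 4 years = 800 person-years (PY). At 0.15 per 100 PY the expected number of first TE events is 800 × 0.0015 = 1.2. The 88% stated there reproduces: on 800 PY at most 2 events keep the Clopper-Pearson upper limit at or below 1 per 100 PY, and the probability of 2 or fewer is 0.8796. That figure concerns the primary crude rate and is not affected.

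The other inputs are **assumed**, because the documents give none: prevalence of any prior history *q*, rate ratio *RR* for history against none, and the share *s* of histories that fall in the one-year window.

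Overstatement of the 'no history' rate = [(1 − q) + q(1 − s)·RR] / (1 − q·s)

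| | Low case | High case |
|---|---|---|
| q, RR, s | 2%, 3, one in four | 10%, 5, one in four |
| Patients with history, of 200 | 4 | 20 |
| Flagged / missed | 1 / 3 | 5 / 15 |
| Overstatement | (196 + 3×3)/199 = 1.03 | (180 + 15×5)/195 = 1.31 |
| True 'no history' rate per 100 PY, overall rate 0.15 | 0.15/(0.98 + 0.02×3) = 0.144 | 0.15/(0.90 + 0.10×5) = 0.107 |
| Observed 'no history' rate | 0.149 | 0.140 |
| Apparent rate ratio | 3/1.03 = 2.91 | 5/1.31 = 3.82 |

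With *s* from 20% to 50% instead, the overstatement runs from (196 + 2×3)/198 = 1.02 to (180 + 16×5)/196 = 1.33.

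In the high case the 'present' stratum falls from 20 × 4 = 80 PY to 5 × 4 = 20 PY. With no events, the exact 95% upper limit (3.689/PY) goes from 4.6 to 18.4 per 100 PY.

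In events, the high-case shift is (0.140 − 0.107)/100 × 780 PY ≈ 0.26.

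**The case against.** The case for leaving the text alone has several parts.

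- **The limit is declared.** Section 8.9.2 describes its reference group as free of TE during the lookback period, not as never having had a TE. This stands: the protocol does not misdescribe the stratum. The stratum still does not separate patients with a prior TE from those without, which is what makes it useful.
- **The anamnestic clause serves another purpose.** It belongs to an inclusion criterion on information before index, and it does not say that earlier records are ignored. A reader might infer that newly enrolled patients get lifetime history and long-enrolled patients get one year. The text does not say that. It follows only if the clause is read into 8.3.2.4, and the protocol does not say whether it should be.
- **Many factors are hardly touched.** Age, sex, BMI, ongoing chronic disease and the items labelled recent are captured adequately in a year. This stands, and it narrows the point to event-type and lifetime history.
- **The SAP will operationalise the variables.** Section 8.3 says so, and the factors are called candidates. But the window is stated in the protocol, so an SAP that follows it inherits the problem.
- **A fixed window is comparable across registries.** All-available history varies in depth. This is a real cost of the change. However, 8.9.2 already concedes that lookback will differ between registries.
- **The numbers are too small to matter.** With about 1.2 expected events, a shift of 0.26 of an event cannot be seen, and upper limits of 4.6 and 18.4 are both far above the threshold of 1 per 100 PY. This stands as to precision. It does not justify the rule: with so few events, whether a patient with a TE had an earlier one is part of reading each case.

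**Conclusion.** The point holds for event-type and lifetime history: previous TE, myocardial infarction, cerebrovascular disease and past cancer. For these, 8.3.2.4 read literally classifies history recorded more than a year before index as absent. 8.9.2 repeats this for prior TE, and the anamnestic clause and the 8.7.3 subgroup are not consistent with it.

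Three stronger readings are not supported:

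- A reader might infer that every older history is lost. The anamnestic clause can admit some of it.
- A reader might infer that patients are placed in an overall group without risk factors. Strata are formed factor by factor.
- A reader might infer that the primary result is biased. The primary crude rate does not use these strata and does not exclude prior TE.

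The overstatement of the 'no history' rate is about 3% to 31% with one in four histories detected. It rests wholly on assumed prevalence, rate ratio and detection. The upper end needs a 10% prevalence, and the 8.9.2 stratum concerns prior TE alone. The stratified rates will be imprecise whichever window is used. This is a worthwhile correction to a secondary objective, not a threat to the study's main estimate.

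**What to change.** Reconcile the risk-factor inclusion criterion (Synopsis and 8.2.6.1), 8.3.2.4, 8.7.3 and 8.9.2:

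- For previous TE and the other event-type or lifetime factors, use all history recorded before index, where the registry holds it, whatever the date of entry.
- Keep the one-year window for transient factors: recent hospitalisation or surgery, trauma or fractures, pregnancy or puerperium, acute infection, hormone therapy.
- Word the prior-TE stratum in 8.9.2 to match, and state whether the 8.7.3 cardiovascular subgroup uses the same history.
- Tabulate the length of available history by registry.
- Keep the one-year version as a sensitivity table.

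The cost is mainly wording, best settled before the first data extraction (planned for Q2 2025), plus one table and one sensitivity output. The downside is that depth of history differs by registry, so some misclassification that varies by registry remains; the tabulation makes it visible. Nor is it assured that the registries hold the data. Section 8.3.2.4 says the feasibility assessment did not cover all risk factors in detail, and Table 6 lists current comorbidities as low in the Canadian registry and pending for HemoNED.

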8. RESEARCH METHODS

8.1. STUDY DESIGN

This is a NI, multi-country, registry-based PASS, longitudinal cohort study based on secondary use of data collected for patients of all ages with moderate congenital HA, without FVIII inhibitors and with severe bleeding phenotype, treated with emicizumab,

The data sources will include registries containing haemophilia patients, primarily based in the European region, but also data sources in the US, Canada and Australia are considered. Data collection will focus on secondary data routinely collected within the registries prior to and after patients initiate treatment with emicizumab. The data sources under consideration are listed in section 8.4. The data will be extracted from the registries annually and pooled to a common data model (CDM) to perform pooled analyses. The planned first data extraction is approximately 1 year after registration of the protocol in the EU PAS register, the study launch. The last data extraction will the date after the last included patient has completed their minimum follow-up of 4 years, Q4 2030. Based on this, the final study report will be submitted as a standalone document in the EU PAS registry. Interim reports will be included in the PSUR/PBRER.

The aim of the study is to include approximately 200 patients who will be followed for a minimum of 4 years from the initiation of emicizumab treatment. According to previous clinical data, this follow-up time will be adequate to observe potential adverse events (AEs) and specifically TE events in the enrolled population (see section 8.6. for details). The overall study duration is expected to last a minimum of 6 years considering a 2-year period from approval of protocol until the end of patient inclusion. However, the overall length of study period will be dependent on MA of emicizumab for moderate patients without FVIII inhibitors. The study length may be adapted to each participating country, and, if needed, the study period may be amended to achieve the targeted sample size (see section 8.5. for details).

Data extracted from the registries will include data that pertains to haemophilia diagnosis, haemophilia disease and treatment history, emicizumab treatment, patient's demographic characteristics, ongoing and previous medication use (whether related to haemophilia or not), and a list of TE risk factors (see section 8.3. for details).

For an overview of the study design and assessment periods see Figure 1.

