Information from feasibility questionnaire or data dictionary: Good = >70% patients included in the disease registries have the required variable, Moderate = 40 - 70% patients with variable, Low <40% patients with variable, Captured = Not disclosed, Not collected = No patients with variable.

The above-mentioned inclusion criteria will ensure that the patient is eligible for the extended indication of emicizumab.

In addition, the patient will have to fulfil the following criteria:

- Initiation of emicizumab treatment during the cohort entry period.
- Information on previous HA outcomes and HA treatments approximately 12 months prior to the index date. In case HA diagnosis occurred within 12 months of the index date, the required lookback period will be shortened to time from HA diagnosis to index date. Anamnestic information capturing historic events but entered in the

Hemlibra—F. Hoffmann-La Roche Ltd

Protocol BO44691, Version 2.0

registry database less than 12 months before the index date will be considered as long as they were recorded prior to the index date.

- Information on risk factors of TE events (e.g., medical comorbidities, treatments and demographic characteristics) approximately 12 months prior to the index date. If the patient is below 1 year of age, the lookback period will be shortened to birth until index date. Anamnestic information capturing historic events but entered in the registry database less than 12 months before the index date will be considered as long as they were recorded prior to the index date.
- Signed the informed consent form where required by local regulations.

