8.3. VARIABLES

A feasibility assessment was conducted between April 2023 and October 2023 to provide input on the availability of the variables in the data sources, the results from the feasibility are detailed in the respective sections. Given that availability of variables varies across registries some variable might require variable derivation. A detailed specification of the operationalisation of all variables will be given in the SAP. A summary of the variables of the study is given in Table 2.

Table 2. Summary list of variables.

Section	Variables	Described in section
Inclusion and exclusion	Diagnosis of congenital HA	8.2.6.1.
criteria	FVIII level	8.2.6.2.
	FVIII inhibitor status	
	Severe bleeding phenotype	
	Initiation of emicizumab treatment	
	Previous treatment with emicizumab	
Exposure	Emicizumab treatment:	8.3.2.2.
	o Start date	
	 Stop date 	
	o Dose	
	o Frequency	
	 Reason for treatment 	
	 Length of treatment 	
	 Reason for discontinuation 	
Censoring variables	Date of death.	8.2.5.
	 End of observation, e.g., due to loss to follow-up, emigration, or disenrollment from the registry. 	
	 Date of emicizumab treatment discontinuation. 	
Safety variables	SAEs	8.3.1. 8.3.2.1.
	 Number of events 	
	o Diagnosis	
	 Start date 	
	o Outcome	
	 Relatedness to treatment 	
	 Treatment of SAE 	
	TE events	
	 Number of events 	
	o Diagnosis	
	 Start date 	
	o Outcome	
	 Relatedness to treatment 	

Hemlibra—F. Hoffmann-La Roche Ltd Protocol BO44691, Version 2.0

Section	Variables	Described in section
	 Treatment of TE event 	
	• TMA	
	 Number of events 	
	o Diagnosis	
	o Start date	
	o Outcome	
	 Relatedness to treatment 	
	 Treatment of TMA event 	
	 Serious systemic hypersensitivity reactions, including anaphylaxis 	
	 Number of events 	
	o Diagnosis	
	o Start date	
	o Outcome	
	 Relatedness to treatment 	
	 Treatment of serious systemic hypersensitivity reaction 	
Patient's demographic	• Age	8.3.2.3.
characteristics	• Sex	
	Ethnicity	
	Weight	
	Height	
	Country of residence	
Patient's haemophilia	Date of diagnosis of congenital HA	8.3.2.3.
related characteristics	Any major complications:	
	o Bleeding	
	o Hemarthrosis	
	 Infections from injections 	
	Prior treatments for haemophilia	

Hemlibra—F. Hoffmann-La Roche Ltd Protocol BO44691, Version 2.0

Section	Variables	Described in section
Medical history	Concomitant medications	8.3.2.3.
	o Start date	
	o End date	
	Other medical history and concurrent conditions	

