	2.1.5 If applicable, that there is no a priori hypothesis?				

Sect	ion 3: Study design	Yes	No	N/A	Section Number
3.1	Is the study design described? (e.g. cohort, case-control, cross-sectional, other design)	\boxtimes			8.1.
3.2	Does the protocol specify whether the study is based on primary, secondary or combined data collection?	\boxtimes			8.2.
3.3	Does the protocol specify measures of occurrence? (e.g., rate, risk, prevalence)	\boxtimes			8.7.
3.4	Does the protocol specify measure(s) of association? (e.g. risk, odds ratio, excess risk, rate ratio, hazard ratio, risk/rate difference, number needed to harm (NNH))			\boxtimes	
3.5	Does the protocol describe the approach for the collection and reporting of adverse events/adverse reactions? (e.g. adverse events that will not be collected in case of primary data collection)				8.3.1, 10.

Comments:

Sect	ion 4: Source and study populations	Yes	No	N/A	Section Number
4.1	Is the source population described?		\boxtimes		8.1. , 8.2.
4.2	Is the planned study population defined in terms of:				8.1. , 8.2.
	4.2.1 Study time period	\square			
	4.2.2 Age and sex		\boxtimes		
	4.2.3 Country of origin	\boxtimes			
	4.2.4 Disease/indication	\boxtimes			
	4.2.5 Duration of follow-up	\square			

Hemlibra—F. Hoffmann-La Roche Ltd

Protocol BO44691, Version

Sect	ion 4: Source and study populations	Yes	No	N/A	Section Number
4.3	Does the protocol define how the study population will be sampled from the source population? (e.g. event or inclusion/exclusion criteria)				8.2.6.

Study has no age restrictions.

Sect	ion 5: Exposure definition and measurement	Yes	No	N/A	Section Number
5.1	Does the protocol describe how the study exposure is defined and measured? (e.g. operational details for defining and categorising exposure, measurement of dose and duration of drug exposure)				8.3.2.2.
5.2	Does the protocol address the validity of the exposure measurement? (e.g. precision, accuracy, use of validation sub-study)			\boxtimes	
5.3	Is exposure categorised according to time windows?	\square			8.3.2.2.
5.4	Is intensity of exposure addressed? (e.g. dose, duration)				8.3.2.2.
5.5	Is exposure categorised based on biological mechanism of action and taking into account the pharmacokinetics and pharmacodynamics of the drug?				8.3.2.2.
5.6	Is (are) (an) appropriate comparator(s) identified?			\square	

Comments:

Sect	ion 6: Outcome definition and measurement	Yes	No	N/A	Section Number

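### Section 8.3.2.4 defines obesity by the adult cut-off of BMI 30 kg/m² in a cohort with no age limit, so most obese younger children would be scored as not obese

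*Protocol*

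**What the plan says.** All references are to the protocol; the SAP is not at hand.

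- **Definition.** Section 8.3.2.4 lists the candidate TE risk factors. One of the 29 entries is "Body Mass Index (BMI) (BMI ≥ 30 kg/m² i.e., obesity". It carries no age condition and no alternative rule for children.
- **Use.** The same section says: "The following candidate variables will be used to characterise the patients TE risk profile and are assessed within one year prior to the index date". For secondary objective 4, Section 8.7.2 says: "The events will be counted for each category/stratum of relevant pre-defined risk factors".
- **Population.** Section 8.1 describes "secondary use of data collected for patients of all ages with moderate congenital HA". A comment in section 4 of the ENCePP checklist adds: "Study has no age restrictions". The inclusion criteria in Section 8.2.6.1 foresee infants: "If the patient is below 1 year of age, the lookback period will be shortened to birth until index date".
- **Deferral.** Section 8.3 says: "A detailed specification of the operationalisation of all variables will be given in the SAP". Section 8.7.1 leaves derivations and category definitions to the SAP, and Section 8.7.2 leaves further detail of the risk factor tables to it.
- **Age subgroups.** Section 8.7.3 names only a split at 50 years. That list is open-ended, but it plans no paediatric group.

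**The concern.** A single BMI threshold of 30 suits adults. In childhood, normal BMI lies below adult values and shifts with age and sex. That is general clinical knowledge rather than something the protocol states. A fixed cut-off of 30 therefore picks out few young children, however obese they are for their age.

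Objective 4 is meant to describe how common the listed TE risk factors are in the treated population and to tabulate first TE events by them. Followed as written, the plan would report too low an obesity prevalence and place some obese children in the not-obese stratum.

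Timing matters a little. Table 7 shows no patient-level access for WBDR and CBDR, and Section 8.6 has such registries apply the CDM themselves and send aggregates. If they return obese and not-obese counts under the adult rule, the analyst cannot re-derive them without asking for a new extraction.

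**Working it through.** The plan states no figure for obesity, so there is nothing to reproduce. The check has four steps.

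**1. What the cut-off demands of a child.** Weight needed for BMI 30 = 30 × height². The heights are illustrative.
- 1.05 m: 30 × 1.1025 = 33.1 kg
- 1.28 m: 30 × 1.6384 = 49.2 kg
- 1.50 m: 30 × 2.25 = 67.5 kg

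A young child can hardly reach these weights. A large adolescent can. So the rule misses most obese younger children, but not every obese patient under 18.

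**2. Direction.** Missed children move from the obese to the not-obese stratum. Prevalence is therefore understated whenever the cohort holds obese children below BMI 30.

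**3. Size, as an illustration only.** The protocol gives N ≈ 200 and an average follow-up of 4 years (Section 8.5.2). It gives none of the following, which are assumptions:
- c, the share of children: 10% to 50%
- p, obesity among children: 5% to 20%
- m, the share of obese children below BMI 30: 50% to 100%
- obesity among adults: 20%

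Patients misclassified = 200 × c × p × m.
- Low: 200 × 0.10 × 0.05 × 0.5 = 0.5
- High: 200 × 0.50 × 0.20 × 1 = 20
- Middle: 200 × 0.30 × 0.15 × 1 = 9

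In the middle case, true prevalence is 0.70 × 0.20 + 0.30 × 0.15 = 18.5% (37 patients). Scored prevalence is 0.70 × 0.20 = 14.0% (28 patients). The obese stratum loses 9/37 = 24% of its patients. The not-obese stratum grows from 163 to 172, or 5.5%.

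**4. Effect on TE rates.** Section 8.5.2 expects 0.15 events per 100 person-years.
- Whole cohort: 200 × 4 = 800 person-years, and 800 × 0.0015 = 1.2 first TE events.
- Misclassified children, at the same rate: from 0.5 × 4 × 0.0015 = 0.003 to 20 × 4 × 0.0015 = 0.12 events.
- Obese stratum, middle case, at the same rate: 37 × 4 × 0.0015 = 0.22 events if scored correctly, against 28 × 4 × 0.0015 = 0.17 as scored. Zero is the likeliest count either way.
- If an event did fall in that stratum and none among the missed children, its rate would be 37/28 = 1.3 times too high. That is small beside the uncertainty of a rate based on one event.

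**The case against.** The strongest reply is that this is SAP detail. The factors are called candidates, the operational definition of every variable is deferred, and Section 8.7.1 expressly leaves category definitions to the SAP. The protocol nowhere says that the cut-off applies to every patient, and a paediatric rule could be added without contradicting any sentence about children. This is fair, and it is why the point is minor. It does not remove the point. Within Section 8.3.2.4 only the availability of the factors is deferred, while the number 30 is printed without qualification for a cohort that includes infants. An SAP that followed the text would apply it to all.

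It can also be said that a stratum labelled BMI 30 or more would be literally correct, and that the protocol does not show that obesity defined by a childhood reference carries the TE risk that put the factor on the list. Both are true. They support the option of limiting the factor to adults. They do not support equating BMI 30 with obesity at every age, which is what the entry does.

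A reader might infer three stronger things that the protocol does not support:
- **That every obese child is missed.** Adolescents at BMI 30 or above are scored as obese.
- **That the TE rates by obesity are materially distorted.** With about 1.2 events expected overall, those rates are nearly uninformative under any cut-off.
- **That the error spoils a comparison between registries or regions.** The study is descriptive and plans no between-registry comparison of obesity. Region is only a subgroup, run or dropped according to patient numbers (Section 8.7.3).

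**Conclusion.** The point holds as a minor one. The stated threshold does not fit the stated population. Most obese younger children would be scored as not obese, which understates obesity in the objective 4 risk profile and puts some obese children in the not-obese stratum.

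Only the direction is established. The range of 0.5 to 20 patients is a 40-fold spread that rests wholly on the assumptions above, and it should not be quoted as an estimate. If few children start emicizumab in this indication, the error is close to nil.

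The primary TE incidence rate and the study size do not use this variable and are unaffected. The effect on TE rates by obesity is negligible. What is affected is one descriptive prevalence under a secondary objective.

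**What to change.** In Section 8.3.2.4, apply BMI ≥ 30 kg/m² only to patients aged 18 or over at index. For younger patients, define obesity by one named age- and sex-specific BMI reference, the same for all registries. Place the rule in the CDM specification before the first extraction, planned for Q2 2025 (Section 5), so that the aggregate-only registries apply it from the start.

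Where a registry cannot supply this, restrict the obesity factor to adults and show patients under 18 as a separate category, not as not obese.

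The cost is small: a sentence or two of text, one extra derivation, and a reference table for the two registries that send only aggregated data. Table 5 shows age, sex, weight and height as collected in all six considered registries, although completeness is not disclosed for UKNHD and HemoNED, nor for sex in WBDR.
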